In spite of the recognition of inflammation as a driver of depression in those with HIV the basic underlying pathophysiology must be elucidated. Prior research investigating plasma inflammatory biomarkers in HIV-infected persons reported an association of depression with pro-inflammatory cytokines, such as interleukin-6 (IL-6), and depression. Yet, factors modulating longitudinal changes in depression with therapy, e.g. group support psychotherapy in HIV patients is poorly understood. We will longitudinally evaluate changes in plasma biomarker changes in participants on ART with standard of care depression interventions before and after implementing group psychotherapy. In Ugandans with HIV, IL-6 in plasma is associated increased risk of depression highlighting the importance of IL-6 and innate inflammation.

Objective

Determine if depression, which persists after depression treatment at 26 weeks, is associated with increased innate inflammation in a prospective cohort of HIV-infected Ugandans receiving SSRIs in which group psychotherapy is initiated.

Hypothesis: Among HIV-infected Ugandans with depression (A): initiating ART and SSRI therapy, structured weekly group psychotherapy coupled with SSRIs will reduce depressive symptoms, measured by the PHQ-9 and Hamilton Depression Rating Scale: (B) Those with persisting depression at 26 weeks will have increased plasma IL-6 and cortisol levels, reflective of ongoing systemic stress response.

Prediction: Innate inflammation (e.g. IL-6) and systemic stress responses (e.g. cortisol) will be higher at 26 weeks in those with persistent depression compared with those with resolved depression.

Experimental Plan:

We will enroll a prospective cohort of HIV-infected subjects with depressive symptoms and a control without depressive symptoms.

- The first 100 subjects - standard of care therapy including SSRI therapy
- The second 100 subjects – standard of care including SSRI therapy + Group Support Psychotherapy
- The third 100 non-depressed subjects- standard of care HIV therapy

We will assess PHQ-9 at baseline (pre-ART) and again at 26 weeks. PHQ-9 instrument has been used and validated in several African countries including Uganda.¹⁻⁹ The cut-offs for the PHQ-9 tool are “not depressed”

(score ≤ 4), “mild depression” (score 5-9), “moderate and moderately severe depression” (score 10-19), or “severe depression” (score ≥ 20).

Enrollment Criteria

- Age ≥ 18 years old and < 65 years

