2. STUDY OBJECTIVES AND ENDPOINTS

2.1. Objectives

- 1) Among depressed HIV-infected Ugandans, determine if the resolution of depression at 26 weeks of HIV therapy is improved with group psychotherapy.
- 2) In the same population determine if persistent depression is associated with higher levels of innate inflammation. Also, compare baseline and follow up inflammation among depressed compared to non-depressed control group.
- 3) Evaluate if viral suppression levels at 26 weeks are improved by group psychotherapy.

Endpoints

- 1) Depression score via patient health questionnaire (PHQ-9) at screening (total screened and total enrolled) and at 26 weeks (total enrolled) comparing those in the observational cohort and those in the intervention cohort.
- 2) Biomarkers associated with depression including IL-6 measured from plasma as well as morning cortisol levels at screening and 26 weeks.

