8. DATA ANALYSIS/STATISTICAL METHODS

8.1. Sample Size Determination

Depression Intervention:

We will power for a reduction in IL-6 between those with persistent and resolved depression at 26 weeks. Based on our systematic review, the reduction in depression score for psychotherapy is 73% from baseline.³² However response rates vary. Another review found the score reduction was 20% when compared to controls.⁴² We then calculated a range of possible sample sizes seen in **Statistics Plan**.

Assuming that 25% of the psychotherapy group will have persistent depression at week 26 (with equal sample sizes, 80% power, and two-sided alpha = 0.05) and I want a delta of .5, we need a total sample size of 168

participants. The prior study had a 22% non-completion rate for group therapy.³⁴ To account for non-completion and up to a 5% loss to follow-up, I estimate a sample size of 200 participants.

Subject Recruitment/Number needed to screen

[figure not shown]
I postulate that the baseline depression rate in these ART naïve subjects would be about 25%.⁴³ Thus we would need to screen 800-1000 HIV+ people.

The non-depressed control group will come out of those screened and not add to the total number screened.

These will be enrolled from the Infectious Disease Institute or three clinics that refer to it. As noted in the preliminary data section, we are currently working on a study in those found clinics and have found we can get about 15 new patients with CD4 <100 cells/uL a month (unpublished data). Our experience is that there are many more presenting with higher CD4 cells/uL counts, or about 150 new individuals a month. Taken these patient sources we estimate we could screen 800-1000 participants over 2.2 years from our 4 clinics and given not all participants will agree to participate we estimate that we can enroll the group over 2.5 years.

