8.2. Analysis of Endpoints

- 1) *Effect of Group Support Psychotherapy:* We will compare the proportion of baseline depression with the proportion of persistent depression at week 26. We will use the PHQ-9 as a continuous variable, with changes from baseline to week 26.
- 2) *Effect of biomarkers on persistent vs. resolved depression:* We will compare those with persistent depression (PHQ-9 ≥ 5 at week 26) versus resolved depression (PHQ-9 < 4 at week 26). We will assess baseline demographic and HIV parameters as well as log₂-transformed plasma cytokines from week 0, week 26, and the change in biomarker values from week 0 to week 26. We will use Benjamini-Hochberg adjustment for multiple comparisons for the biomarkers unrelated to our *a priori* hypothesis (i.e. IL-6 association with persisting depression). If the distribution between groups is unbalanced for an important factor (e.g. age, sex as biological variable, anti-depressant use, HIV viral load), we will adjust as needed for differentially distributed variables between the cohorts. We will consider sex as a biological variable in our analyses, considering differential effects in women vs. men.
- 3) *Effect of biomarkers on depressed vs non-depressed control group:* We will compare those never depressed (PHQ-9 < 5) and those depressed at baseline and at 26 weeks. We will also group those never depressed with those with resolved depression (PHQ-9 < 5 at week 26) and compare with those with persistent depression (PHQ-9 > 4 at week 26). We will assess baseline demographic and HIV parameters as well as log₂-transformed plasma cytokines from week 0, week 26, and the change in biomarker values from week 0 to week 26. We will use Benjamini-Hochberg adjustment for multiple comparisons for the biomarkers unrelated to our *a priori* hypothesis (i.e. IL-6 association with persisting depression). If the distribution between groups is unbalanced for an important factor (e.g. age, sex as biological variable, anti-depressant use, HIV viral load), we will adjust as needed for differentially distributed variables between the cohorts. We will consider sex as a biological variable in our analyses, considering differential effects in women vs. men.

*Depression Defined as PHQ-9 score 5-19 (severely depressed excluded)

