8.3. Safety Analysis

Data and Safety Monitoring Plan

1.0 Introduction: This document describes the Roles and Responsibilities of the Data Monitoring Committee (DMC) convened to monitor the clinical study.

2.0 Composition: This DMC shall have the composition described below. As DMC meetings will be at least annually, the DMC shall have a quorum minimum of three members and the statistician to be required for each DMC meeting. All members have previous experience with clinical trials and/or clinical studies experience with cryptococcal meningitis (Table 1). As the intervention is an open label study, members of the team will participate in the DMC along with external members.

Table 1. DMC Membership

Name	Role	Relevant Experience
[name]	Statistician	Multiple HIV-related trials, U of MN
[name], PhD	Member	Psychiatrist, U of MN
[name], MMed	Member	Multiple clinical trials, Mbarara Univ.
[name]	Member	Multiple AIDS-related clinical trials, Mbarara Univ.
[name]	Member	Epidemiologist, U of MN

Additional observers will participate as possible. Observers are non-voting members of the DMC. Observers will receive communications on DMC reports and recommendations.

3.0 Roles and Responsibilities: It is the role of the DMC to protect trial subjects and to provide impartial advice and assistance to the Principal Investigator regarding the conduct and continuation of the study, so as to protect the validity and credibility of the trial. The DMC will have access to the clinical protocol, interim data, adverse event reports, clinical monitoring reports, annual and/or progress reports submitted to the IRB and/or Regulatory Agency, and correspondence between the Principal Investigator and either the IRB or any Regulatory Agency of competent jurisdiction.

The specific roles of this DMC will be as follows:

- Assess data quality, including completeness.
- Monitor compliance with the protocol by participants and investigators.
- Monitor recruitment progress and losses to follow-up.
- Monitor evidence for treatment differences in the main efficacy outcome measures.
- Monitor evidence for treatment harm (SAE's).
- Advise on protocol modifications suggested by investigators or sponsors.
- Recommend trial continuation or termination as appropriate.

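### No primary contrast is named: the synopsis and sample size point to IL-6, the first objective and endpoint point to psychotherapy, and the psychotherapy effect has two unranked measures

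*Combined protocol and SAP*

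**What the plan says.** The documents give different answers on which question decides the study.

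- **Synopsis, Objective.** There is a single objective, the inflammation question: "Determine if depression, which persists after depression treatment at 26 weeks, is associated with increased innate inflammation".
- **Section 2.1.** Objective 1 is psychotherapy: "determine if the resolution of depression at 26 weeks of HIV therapy is improved with group psychotherapy". Inflammation is Objective 2. Endpoint 1 is the PHQ-9 score, observational versus intervention cohort; biomarkers are Endpoint 2.
- **Section 2.2.** Hypothesis A (psychotherapy) and Hypothesis B (IL-6 and cortisol) stand side by side.
- **Section 8.1.** The sample size falls under a depression-intervention subheading, but the contrast sized is IL-6: "We will power for a reduction in IL-6 between those with persistent and resolved depression at 26 weeks". The only error rate in the documents is here: "two-sided alpha = 0.05".
- **Section 8.2, item 1 (psychotherapy).** "We will compare the proportion of baseline depression with the proportion of persistent depression at week 26", followed by "We will use the PHQ-9 as a continuous variable, with changes from baseline to week 26". No test, level or order is given for either.
- **Section 8.2, items 2 and 3.** Benjamini-Hochberg covers the biomarkers outside the a priori IL-6 hypothesis. Only the baseline cytokine and virologic analyses are labelled secondary.
- **Section 8.3.** The DMC is to "Monitor evidence for treatment differences in the main efficacy outcome measures". No section says which measures these are.

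**The concern.** With no named primary, the choice of headline can be made after the results are known. A report could lead with IL-6 because it is the powered contrast, or with psychotherapy because it is Objective 1.

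Within the psychotherapy question, the proportion and the mean score can differ on significance, and the plan does not say which one answers Objective 1. The proportion has a further problem: read literally, it is a before-and-after comparison that does not involve the other cohort.

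At stake are an inflated chance of a false claim and an argument over what the study showed. The DMC also has no identified measure to monitor.

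**Working it through.** **1. Which test owns the stated alpha.** Inputs from 8.1: two-sided 0.05, 80% power, delta 0.5, 25% persistent. No SD is given, so I read delta as 0.5 SD. With a 1:3 split of persistent to resolved:

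n(persistent) = (1 + 1/3) × (1.960 + 0.842)² / 0.5² = 41.9, rounded up to 42; n(resolved) = 3 × 42 = 126; total 168.

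This is the plan's figure exactly. An equal split of persistent and resolved would give 63 + 63 = 126, so the phrase "with equal sample sizes, 80% power" must refer to the two cohorts. The full 0.05 is therefore used by the IL-6 contrast. Nothing in 8.1 or 8.2 assigns a level to either PHQ-9 measure.

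**2. The proportion comparison as worded.** Inclusion criterion 4 in 3.1 requires a PHQ-9 of 5 to 19, and the note in 8.2 defines depression by the same range. The baseline proportion is therefore 100% in both depressed cohorts. Section 1.2 reports 38% persistence (28/73) at 2 years on HIV therapy alone in one Ugandan cohort. A fall from 100% is thus expected without psychotherapy, and only a comparison between cohorts addresses Objective 1.

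**3. False-positive rates.** Assume both PHQ-9 measures are tested between cohorts at 0.05 and that there is no true difference. The documents give no correlation r between the two tests, so a range is shown. P2 is the chance that at least one PHQ-9 test is significant (bivariate normal). Adding an independent IL-6 test gives P3 = 1 − (1 − P2) × 0.95.

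| r | P2 | P3 |
|---|---|---|
| 0.9 | 7.0% | 11.7% |
| 0.7 | 8.3% | 12.9% |
| 0.5 | 9.1% | 13.6% |

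The outer limits are 5% and 9.75% if the PHQ-9 tests are identical (1 − 0.95²), and 9.75% and 14.3% if all tests are independent (1 − 0.95³).

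**4. How often the two measures disagree.** None of these inputs is in the documents: 95 per cohort (100 less 5% loss), baseline about 9 (SD 3.3) limited to 5–19, observational week-26 mean 4, slope 0.4 on baseline, residual SD 4. The tests are a t-test on change and a z-test on PHQ-9 of 5 or more, with 6,000 simulated trials per setting.

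| True difference (points) | Power, score | Power, proportion | Disagree on significance |
|---|---|---|---|
| 1 | 30% | 25% | 25% |
| 1.5 | 56% | 49% | 29% |
| 2 | 80% | 74% | 23% |
| 3 | 98% | 97% | 4% |

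With no true difference, either test is significant in about 9% of trials, in line with step 3. With residual SD 3, disagreement is 34%, 28%, 11% and under 1% at the same four differences.

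**5. What each remedy costs the IL-6 test.** Kept alone at 0.05, it needs 168 evaluable (power 80.1%). At 0.025 it needs 51 + 153 = 204, and power at 168 falls to 71.4%. At 0.0167 it needs 56 + 168 = 224, and power at 168 falls to 66.0%.

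**The case against.** The strongest reply is that IL-6 is primary in all but name. It is the only synopsis objective, the powered contrast and the stated a priori hypothesis. Endpoint 1 is the only endpoint that names a cohort comparison, so a DMC could reasonably take it as the efficacy measure. This is fair, and it supports the choice of IL-6 below. It does not close the gap, because psychotherapy is still Objective 1, Endpoint 1, Hypothesis A and analysis item 1.

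A second reply is that psychotherapy and IL-6 are separate questions, one about an intervention and one about an association, so a joint error rate is not obligatory. That also stands. The 12% to 14% applies only to a reader who treats them as one family; for psychotherapy alone the figure is 7% to 9%.

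A reader might infer that three tests each stand at a full 0.05 and that the trial may be declared positive on any of them. The documents do not support this. They state 0.05 for IL-6 only, give no success rule, and do not word item 1's proportion as a between-cohort test. Nor is three a firm count: item 2 assesses cytokines at week 0, at week 26 and as change.

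The disagreement rate depends on assumed PHQ-9 distributions and nearly vanishes at a 3-point difference. At 1 to 2 points the simulated persistence under psychotherapy is 36% to 27%, above the 25% planned in 8.1, so the plan's own expectation lies towards the end where disagreement is less frequent.

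Section 8.1 also refers to a range of sample sizes in material not reproduced in the text I had. I rely only on the sentence that yields 168.

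**Conclusion.** The point holds as a gap in specification. No contrast is primary, the sections disagree on which question leads, item 1 has two unranked measures, and its proportion comparison as worded cannot show a psychotherapy effect.

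If both PHQ-9 measures are tested between cohorts at an assumed 0.05, the chance of a false psychotherapy claim is about 7% to 9% for correlations of 0.9 to 0.5. With IL-6 in the same family, taken as independent, it is about 12% to 14%. These figures assume no other difference between the sequentially enrolled cohorts. Under the base assumptions, the two measures disagree in roughly a quarter of trials at 1 to 2 points and rarely at 3. The specification gap does not depend on that rate.

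**What to change.** In 2.1 and 8.2:

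- **Primary:** week-26 log2 IL-6, persistent versus resolved depression, two-sided 0.05. This is the contrast that 8.1 powers and the synopsis states. Label week-0 IL-6 and change in IL-6 secondary. Use one cut-off throughout: 8.2 item 2 leaves a score of exactly 4 in neither group, while the synopsis counts it as resolved.
- **Key secondary, psychotherapy:** the continuous week-26 PHQ-9 score, observational versus intervention cohort, matching Endpoint 1. State that it answers a separate question for which the trial was not sized.
- **Supportive:** the between-cohort proportion with persistent depression, with a 95% CI and no separate claim. This replaces the baseline-to-week-26 comparison.
- **No gating** of psychotherapy on IL-6. A gate would make Objective 1 depend on an unrelated association: with 80% power for IL-6 and about 80% for the score (the 2-point case), a formal psychotherapy claim would have a chance of only about 0.80 × 0.80 = 64% if the tests are independent.
- **DMC plan (8.3):** refer to the named psychotherapy contrast.

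The cost is a few sentences, with no added participants or data; the evaluable number stays at 168, whereas splitting alpha would need 204 to 224. There are two drawbacks. A result significant only on the proportion can no longer be the headline. And because Objective 1 speaks of resolution, its wording must be aligned with a score-based deciding measure.

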1) Effect of Group Support Psychotherapy: We will compare the proportion of baseline depression with the proportion of persistent depression at week 26. We will use the PHQ-9 as a continuous variable, with changes from baseline to week 26.

2) Effect of biomarkers on persistent vs. resolved depression: We will compare those with persistent depression (PHQ-9 > 4 at week 26) versus resolved depression (PHQ-9 < 5 at week 26). We will assess baseline demographic and HIV parameters as well as log2-transformed plasma cytokines from week 0, week 26, and the change in biomarker values from week 0 to week 26. We will use Benjamini-Hochberg adjustment for multiple comparisons for the biomarkers unrelated to our a priori hypothesis (i.e. IL-6 association with persisting depression). If the distribution between groups is unbalanced for an important factor (e.g. age, sex as biological variable, anti-depressant use, HIV viral load), we will adjust as needed for differentially distributed variables between the cohorts. We will consider sex as a biological variable in our analyses, considering differential effects in women vs. men.

3) Effect of biomarkers on depressed vs non-depressed control group: We will compare those never depressed (PHQ-9 <5) and those depressed at baseline and at 26 weeks. We will also group those never depressed with those with resolved depression (PHQ-9 <5 at week 26) and compare with those with persistent depression (PHQ-9 >4 at week 26). We will assess baseline demographic and HIV parameters as well as log2-transformed plasma cytokines from week 0, week 26, and the change in biomarker values from week 0 to week 26. We will use Benjamini-Hochberg adjustment for multiple comparisons for the biomarkers unrelated to our a priori hypothesis (i.e. IL-6 association with persisting depression). If the distribution between groups is unbalanced for an important factor (e.g. age, sex as biological variable, anti-depressant use, HIV viral load), we will adjust as needed for differentially distributed variables between the cohorts. We will consider sex as a biological variable in our analyses, considering differential effects in women vs. men.

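### The IL-6 comparison that sizes the trial uses the week-26 PHQ-9 only as a cut near 5; pre-specifying a regression on the recorded score would be a cheap gain for most graded relations, though not for a threshold.

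*Combined protocol and SAP*

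**What the plan says.** Section 8.1 names the comparison that sets the sample size: "We will power for a reduction in IL-6 between those with persistent and resolved depression at 26 weeks". Its inputs are "Assuming that 25% of the psychotherapy group will have persistent depression at week 26", "80% power, and two-sided alpha = 0.05" and "I want a delta of .5, we need a total sample size of 168".

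Section 8.2 item 2 defines the two groups from the week-26 PHQ-9: "We will compare those with persistent depression (PHQ-9 ≥ 5 at week 26) versus resolved depression (PHQ-9 < 4 at week 26". Item 2 of the synopsis's Statistical Analysis has the same comparison with slightly different limits: "We will compare those with persistent depression (PHQ-9 > 4 at week 26) versus resolved depression (PHQ-9 < 5 at week 26". Both places name the association of IL-6 with persisting depression as the a priori hypothesis and exempt it from the Benjamini-Hochberg adjustment.

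The schedule of events has the PHQ-9 and the plasma biomarkers both measured at week 26. Item 1 of section 8.2, on the effect of psychotherapy, already keeps the score whole: "We will use the PHQ-9 as a continuous variable, with changes from baseline to week 26". No item does so for IL-6 or any other biomarker.

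**The concern.** Once the score is cut, a participant scoring 5 counts the same as one scoring 19, and a 0 counts the same as the top of the resolved range. If IL-6 rises gradually with symptoms, that variation is informative and the two-group test discards it. The expected 25:75 split costs further precision.

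Elsewhere the plan treats depression as graded. It bands the PHQ-9 by severity. The baseline cytokine analysis in section 8.2 compares mild with moderate-or-above depression, which makes sense only if biomarkers may differ among people who all score at least 5. The background section links falling psychological symptoms to falling cortisol. No section argues for an IL-6 threshold at a score of 5.

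At stake is the chance of missing a true association on the one comparison the trial is sized for, using data that will be collected anyway.

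**Working it through.** **Inputs from section 8.1.** Total 168, 25% persistent, delta 0.5, two-sided alpha 0.05, power 80%. No unit is given for delta. It is read here as within-group SD units, because that reproduces 168.

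**Reproducing 168.** With a 1:3 split, the smaller group needs (1.96 + 0.84)² × (1 + 1/3) / 0.5² ≈ 41.9, so 42. Then 42 + 126 = 168. The normal approximation gives 80.1% power and the t-test 79.7%. A 1:1 split would need only 126, so the phrase "with equal sample sizes, 80% power" cannot describe persistent versus resolved. The 168 follows only if 25:75 is the split of the whole comparison.

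**More analysed.** The plan enrols 200 depressed participants and allows up to 5% loss: 200 × 0.95 = 190. The two-group t-test then has about 84% power.

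**From the split to the full score.** A difference of 0.5 SD at 25:75 is a correlation between IL-6 and the group indicator of 0.5 / √(0.25 + 1/0.1875) = 0.212. If IL-6 is linear in the score, its correlation with the score is 0.212 / k, where k is the correlation between the score and its own cut. Power at n = 168 is then Φ(atanh(r) × √165 − 1.96). The documents do not give the score distribution, so k is an assumption:

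| Assumed score | k | r with score | Power |
|---|---|---|---|
| Normal | 0.734 | 0.288 | 96.8% |
| Exponential | 0.800 | 0.264 | 93.6% |
| Negative binomial integers, 25% at 5 or more | 0.784-0.826 | 0.256-0.270 | 92.0-94.4% |

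**If IL-6 only steps up at 5.** The correlation with the score becomes 0.212 × k. With k = 0.807 this is 0.171, and power is Φ(0.172 × 12.85 − 1.96) ≈ 60%.

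**Other shapes, by simulation.** Scores were skewed integers (a scaled gamma rounded down, shape 0.5, 1 or 2) with 25% at 5 or more and n = 168. The difference between 5-or-more and below 5 was held at 0.5 within-group SD throughout. Each range runs over the three score shapes, and repeat runs move the figures by about a point.

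| True relation of IL-6 to PHQ-9 | Two-group test | Regression on raw score |
|---|---|---|
| Linear | 78-80% | 92-93% |
| Linear in log(score + 1) | 78-80% | 87-96% |
| Linear, then flat above 10 | 78-80% | 81-91% |
| Linear, then flat above 7 | 78-80% | 76-89% |
| Step at 5 only | 78-80% | about 60% |

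**Break-even.** With exponential integer scores, part of the group difference was made a pure jump at 5 and the rest linear. Two-group versus regression power was 80% v 88% with a quarter as jump, 79% v 80% with half, and 80% v 73% with three quarters. For this mixture the regression does at least as well until about half the difference is a jump at that one point.

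**The case against.** The strongest reply is that the plan tests the question it asks. The objective, hypothesis B and the prediction are all worded as persistent versus resolved depression. The cut is the protocol's own boundary for not depressed (4 or below), not one chosen from data. A slope draws partly on variation among people scoring 0 to 4, so it does not by itself show that persistent cases have higher IL-6. This stands. It is why the two-group comparison should remain a reported test and not shrink to a descriptive summary.

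The size of the gain is also conditional. A raw-score regression can lose to the split without an exact step at 5: a plateau at 7 can take it to 76%. Under a pure step the loss, from about 79% to 60%, is at least as large as the gain under linearity. This stands too. A rank correlation would not rescue the gain: with skewed scores and a linear relation it had only 79-89% power.

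Finally, 80% may understate the planned test. With 190 analysed it is 84%. The 25% is stated for the psychotherapy group only, and section 1.2 reports persistence of 25% to 38% in other cohorts. If the pooled share were 31% (an assumption), power would be 85% with 168 and 89% with 190. The same uncertainty runs the other way: at 20% persistent it is 73%, and at 15% it is 63%, both with 168.

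A reader might infer that the cut throws away half the information, that the full score would give 97% power, or that about 92 people would do. Those figures all need a normally distributed score. With 75% expected below 5 on a 0-27 integer scale, a floor is far more likely. Under the negative binomial scores the cut retains about 0.61 to 0.68 of the information (k²), and 80% power needs roughly 105 to 118 people.

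**Conclusion.** The point holds as a recommendation. The comparison that sizes the trial uses the week-26 PHQ-9 only through a cut, and no item uses the recorded score for any biomarker. With the plan's own inputs the two-group test has about 80% power. Regression on the score in the same 168 adds roughly 12 to 15 points if the relation is linear with skewed scores. It usually gains under a log shape, may gain or lose a little under a plateau, and loses nearly 20 points under a step at 5.

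This rests on delta being 0.5 within-group SD, on 25:75 describing all depressed participants, and on assumed score distributions and relation shapes. The documents neither assert nor deny a graded relation.

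They do not support calling the dichotomy an error. It tests the stated hypothesis at conventional power. The two versions of the cut are a separate, smaller matter: as printed in section 8.2 item 2, a score of 4 belongs to neither group, whereas in the synopsis it counts as resolved.

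**What to change.** 1. In section 8.2 item 2 and synopsis item 2, pre-specify a linear regression of week-26 log2 IL-6 on the continuous week-26 PHQ-9 score, in all depressed participants with both measures, as a test of the a priori IL-6 hypothesis.
2. Keep the persistent versus resolved comparison, with its test and confidence interval, as the direct answer to the hypothesis as worded. Use one cut in both places that leaves no score unassigned.
3. State in advance which of the two tests carries the a priori claim. Otherwise the unadjusted hypothesis has two chances at the 5% level.
4. Note in section 8.1 that the 80% figure refers to the two-group test.

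The cost is wording; no new data, visits or participants are needed. The slope is expressed per PHQ-9 point (or per 5 points), which is less direct than a group difference, and it loses power if IL-6 changes only at the cut. If the regression is chosen to carry the claim, the team accepts that risk; the retained comparison would show such a pattern but would not carry the claim.
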